2.2. Endpoints

2.2.1. Primary Endpoints

The primary endpoints are:

- The number and percentage of study participants who experience solicited local and systemic reactions during the 7 days after administration of investigational M2SR vaccine or placebo, as recorded through subject electronic diary (eDiary).
- The number and percentage of study participants who experience unsolicited AEs during the 28 days after administration of investigational M2SR vaccine or placebo and prior to administration of licensed QIV.
- The number and percentage of study participants who experience SAEs from the time of informed consent through 28 days after receipt of QIV.

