7.4. Removal of Subjects from the Study

Subjects have the right to withdraw from the study at any time for any reason, including personal reasons. A subject can withdraw without giving a reason. The Investigator should however try to determine why a subject withdraws from the study and document the reason for withdrawal in the source documents and in the EDC system.

Subjects may be withdrawn from the study in the event of:

- Meeting any of the halting rules in Section 7.3
- A severe AE or SAE;
- Difficulties in obtaining blood or other samples;
- Failure of the subject to comply with the protocol requirements or to cooperate with the Investigator.

Subjects must be withdrawn from the study in the event of:

- Withdrawal of consent
- Lost to follow-up
- Death
- Termination of the study by the Sponsor (described in Section 7.2)
- For safety reasons, it being in the best interest of the subject that he/she be withdrawn, in the Investigator's opinion;
- A positive pregnancy test (the subject or, if reported by a male subject, his female partner), or if the subject/partner is non-compliant with the contraception requirements (see Section 4.1);
- Lab confirmed infection with SARS-CoV-2
- Development of a medical condition that requires concomitant treatment with a prohibited therapy (see Section 5.9.2);
- Breaking of the randomization code during administration of the study drug. If the code is broken for safety reporting purposes, the subject may remain in the study; however, in such cases subject and site staff will remain blinded to IP treatment.

The monitor and Sponsor will be informed in the event of a subject being withdrawn from the study. In case of withdrawal due to an SAE (for details on AE reporting see Section 9.5), the Sponsor should be notified within 24 hours; in case of withdrawal for other reasons; the Sponsor should be notified within 2 days from the event.

Subjects who are withdrawn from the study prior to completion of the scheduled study procedures for any reason (AE, withdrawal of consent, etc.) should be contacted by phone for a safety follow-up 4 weeks after vaccination. In case of an AE, the appropriate follow-up will be done.

Subjects who are withdrawn from the study will not be replaced.

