2.1.1.2. IP Safety Set (IPSS) Population

This SS Population will consist of all randomized subjects who receive any IP administration. Safety results will be presented by actual treatment received.

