2.1.1.4. IP Evaluable Set (IPEVAL) Population

The IP Evaluable Set will consist of all randomized subjects who receive an IP administration, have an IP Day 29 visit with sample collection, and have no major protocol violations/deviations thought to interfere with evaluation of IP immunogenicity. Results for this set will be reported by randomized treatment. If more than 5% of this population is excluded due to major protocol deviations, then a new set (IPPPEVAL) will be formed, and analyses repeated using this population.

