9. PRIMARY OBJECTIVE: SAFETY EVALUATION (IPSS)

9.1. Extent of Exposure

IP exposure will be characterized as recorded on the eCRF. The protocol references actual dose, percentage of expected dose, and percentage of subjects receiving expected dose. The protocol also references vial weights. The eCRF captured only whether complete dose was administered. IP exposure will be reported as IP administered.

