9.2.1. Reactogenicity Assessments: eDiaries

Temperature (degrees celsius or fahrenheit to one decimal point), 7 systemic reactogenicity symptoms and 2 local reactions were collected pre-dose and once daily for the 7 days following IP administration via a reactogenicity eDiary, see Protocol Appendix 1. Symptoms were reported by the subject, at 5 levels of intensity (0=None, 1=Mild, 2=Moderate, 3=Severe, 4= Medically attended).

Investigators (or designee) were required to review the reactogenicity eDiary data daily as part of the ongoing safety review. The site was to be notified if a subject had entered a Grade 3/4 severity for a symptom. The site was then required to contact the subject to confirm the scoring and determine whether subject should attend the clinic for further follow-up. The Investigator was required to evaluate the symptoms and assess whether they agree with the grading of 3 or higher. Regardless of the PI assessment, the diary entries were not to be changed, and the Investigators were to either verify the patient-recorded score or note a discrepancy in the source documentation. If any discrepancies or changes in reporting were noted at review, both uncorrected and corrected data were to be recorded and both sets of symptom scores transferred from the eDiary vendor. Corrected eDiary data will be summarized in the CSR. Original data entries as recorded by the patient and/or where these differ from final reports will be given in an appendix to the CSR. Missing eDiary data will be reported as missing; no symptom values were to be imputed.

Daily temperatures and worst (maximum) temperature over the 7 days experienced by each subject will be summarized using descriptive statistics.

Worst symptom severity experienced over the 7 days and the number of days with any grade of symptom (score > 0) will be summarized using frequencies and percentages.

These summaries will use the IPEVAL set.

Symptoms tables include both local reactions and systemic symptoms.

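### SAP 9.2.1 tabulates the first primary safety endpoint, solicited reactions over 7 days, on the Day 29 immunogenicity set (IPEVAL) instead of on all dosed subjects (IPSS)

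*SAP*

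**What the plan says.** Protocol 2.2.1 lists as its first primary endpoint "The number and percentage of study participants who experience solicited local and systemic reactions during the 7 days" after vaccine or placebo, recorded by eDiary. Protocol 8.1 puts anyone who receives IP in the safety set.

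SAP Section 9 is headed "PRIMARY OBJECTIVE: SAFETY EVALUATION (IPSS"). SAP 2.1.1.2 defines that set: "This SS Population will consist of all randomized subjects who receive any IP administration", and adds "Safety results will be presented by actual treatment received".

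Within Section 9, however, SAP 9.2.1 describes the eDiary summaries (daily and worst temperature, worst symptom severity, days with symptoms) and ends: "These summaries will use the IPEVAL set". Under SAP 2.1.1.4, subjects in IPEVAL must have received IP and must also "have an IP Day 29 visit with sample collection, and have no major protocol violations/deviations thought to interfere with evaluation of IP immunogenicity". The same section says "Results for this set will be reported by randomized treatment".

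SAP Section 1 gives the SAP precedence over the protocol. No part of the SAP plans an IPSS version of the eDiary tables, and SAP Section 12, on changes to planned analyses, does not mention the choice.

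**The concern.** The diary window closes about three weeks before Day 29. A subject can be dosed, complete every diary entry, and still vanish from the reactogenicity tables for want of a Day 29 visit or sample. That condition serves immunogenicity and has no bearing on whether the subject had a reaction in the first week.

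The loss need not be random. Protocol 7.4 allows withdrawal for a severe AE or SAE, and requires it for "Lab confirmed infection with SARS-CoV-2". The blood and nasal samples taken at an Early Termination visit (Protocol 6.1.4) do not make that visit a Day 29 visit. If subjects with bad post-dose symptoms are more likely to leave, severe reactions would be understated.

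Safety is the only primary objective, and Protocol 1.4 describes this as the first assessment of M2SR vaccines in an older population. Severe reactions would be few, so one or two missing subjects could change how the table reads.

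**Working it through.** **1. The two sets side by side**

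| | IPSS (SAP 2.1.1.2) | IPEVAL (SAP 2.1.1.4) |
|---|---|---|
| Received IP | required | required |
| Day 29 visit with sample | not required | required |
| No major deviation thought to affect IP immunogenicity | not required | required |
| Grouping | actual treatment | randomized treatment |
| Used for | Section 9 heading (safety) | eDiary tables in 9.2.1 |

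The specific sentence in 9.2.1 would govern the programming of these tables, and the SAP overrides the protocol. The conflict is therefore real and is not settled by the section heading.

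**2. The plan's own figure**

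The one probability behind the sample size is in Protocol 1.4: more than 95% chance of seeing an AE of 20% prevalence in 15 subjects. Check: 1 − 0.8^15 = 0.965, which agrees. It does not depend on the analysis set, and the documents give no figure for loss before Day 29. What follows uses the planned 80 active subjects and assumed losses.

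**3. Effect on the observed rate**

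Let x of n dosed subjects react, and let k be excluded, of whom r are reactors. The IPSS rate is x/n and the IPEVAL rate is (x − r)/(n − k). The IPEVAL rate is lower when r/k > x/n and higher when r/k < x/n. All counts below are assumptions.

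| Reactors, IPSS | Excluded | Of these, reactors | IPEVAL |
|---|---|---|---|
| 4/80 = 5.0% | 2 | 2 | 2/78 = 2.6% |
| 4/80 = 5.0% | 4 | 4 | 0/76 = 0.0% |
| 8/80 = 10.0% | 4 | 4 | 4/76 = 5.3% |
| 8/80 = 10.0% | 4 | 0 | 8/76 = 10.5% |

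The direction depends on who leaves. Loss concentrated in reactors can halve or erase a small rate. Loss of non-reactors raises the rate slightly.

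**4. Effect on precision**

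With zero events, the exact two-sided 95% upper bound is 1 − 0.025^(1/n):

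- n = 80 (no loss): 4.5%
- n = 76 (4/80 = 5% lost): 4.7%
- n = 72 (8/80 = 10% lost): 5.0%

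The smaller denominator matters little. What matters is whether the exclusions are selective.

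**5. Do other outputs recover the endpoint?**

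SAP 9.2 leaves it to the investigator whether a diary symptom becomes an AE, and says the two sources were not reconciled. Protocol 6.2.4 says diary data need not be entered separately as AEs. The AE tables therefore cannot stand in for the number and percentage of subjects with solicited reactions.

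**The case against.** The strongest reply is that this is a labelling slip in a descriptive study. There are no hypothesis tests, AE rates are not compared statistically, and nobody knows that anyone will be excluded. IP is a single dose, so a bad reaction gives no later IP dose to refuse, and withdrawal for a severe AE or SAE is discretionary. There are also partial safeguards. Reasons for exclusion from evaluable sets are listed (SAP 3). All AEs are listed, with separate listings of deaths, SAEs and discontinuations due to AEs, and AEs within 7 days of IP are reported (SAP 9.2). Graded fever appears in the vital-sign shift tables (SAP 9.4). Original diary entries go to a CSR appendix (SAP 9.2.1). A severe reactor who left should not be wholly invisible.

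Much of this stands, and it limits how far the point can be pushed. Four stronger readings are tempting:

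- *The reported rate is biased downward.* The withdrawal rules make this possible. The documents do not show it, and the last row of the rate table goes the other way.
- *The SARS-CoV-2 rule removes subjects because of their symptoms.* Swabs at screening, V01 and V02 are taken from everyone, and the V01 and V02 samples are batch tested. Symptom-triggered swabs are additional, and Covid-19 symptoms are not vaccine reactions.
- *Every major deviator drops out, for reasons arising after the diary window.* SAP 2.1.1.4 limits exclusion to deviations thought to affect IP immunogenicity, although SAP 4 is worded more broadly. Some deviations, such as dosing errors, arise at or before dosing. The provision for a further per-protocol set leaves it unclear how many deviators IPEVAL itself removes.
- *A mis-dosed subject would be counted in the wrong arm.* Receiving the wrong product could well be judged to affect immunogenicity, so the subject may be excluded instead. No mis-dosing is documented.

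None of this gives a reason to tabulate a 7-day safety endpoint on a Day 29 immunogenicity set. The safeguards do not supply the endpoint.

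**Conclusion.** The sentence is wrong as written. It takes a primary safety endpoint off the set that the SAP's own heading, the SAP's definition of the safety set and the protocol all assign to safety, and nothing in the SAP explains why. Dosed subjects with usable diary data would be left out if they lack a Day 29 visit with a sample or have a major deviation judged to affect immunogenicity.

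The consequence is a possible selection bias of unknown size and direction. Understating severe reactions is the outcome to guard against, but it is a risk and not a demonstrated result. If nobody is excluded, the effect is zero. The illustrative figures rest on the planned 80 active subjects and on assumed numbers of reactors and exclusions. Only the eDiary summaries are affected; unsolicited AEs and SAEs remain under the IPSS heading.

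**What to change.** Replace the sentence in SAP 9.2.1 with:

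*These summaries will use the IPSS, by actual treatment received; the number of subjects with post-dose eDiary data will be shown as the denominator and missing diaries reported as missing.*

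This keeps the rule already in 9.2.1 that missing diary data are not imputed, and it makes any diary non-response visible. Keep IPEVAL for immunogenicity, or at most show the diary tables on it as a supportive display.

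The cost is one sentence in the SAP and a change of population flag and treatment variable in the table shells. No new data are needed.

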9.3. Clinical Laboratory Evaluation

Clinical safety labs are collected pre-IP administration. There are no scheduled safety lab collections after IP administration except as ordered/requested by the investigator or safety/medical monitor for specific diagnostic or AE follow-up. Any laboratory-based AEs will be reported based on the Grading Scale for Laboratory AEs – Modified from FDA GradingScale as Appropriate for Local Lab (Protocol Appendix 4).

A listing of clinical laboratory test results (screening and as-requested) will be provided. Results will be flagged as outside reference ranges and, where appropriate, graded according to the FDA Grading Scale (see protocol Appendix 3 & 4). Clinically significant (CS) values or CS changes from baseline values were to be recorded as AEs.

9.4. Vital Signs

Blood pressures, heart rate, respiratory rate and temperature will be summarized at each time point by descriptive statistics for the result and for the change from baseline (IP and then QIV baseline).CS values or CS change from Baseline were recorded as AEs at the discretion of the clinical investigator.

Vital signs were graded according to the FDA Guidance for Industry: Toxicity Grading Scale for Healthy Adult and Adolescent Volunteers Enrolled in Preventive Vaccine Clinical Trials, September 2008, and noted as clinically significant. Vital signs to be assessed include: fever, tachycardia, bradycardia, systolic and diastolic hypertension, diastolic hypotension, and respiratory rate. These VS will be reported by shift tables of worst grade recorded post IP administration through QIV Day 29.

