6.2.1.5. Vital Signs

Vital signs include oral temperature (°C), blood pressure (mmHg), pulse rate (beats per minute). Vital signs will be obtained at the time points specified in the Schedules of Events (Table 2 and Table 3). Blood pressure will be measured from the subject's arm after the subject has been seated or semi-recumbent for approximately 5 minutes with the arm supported at the level of the heart. Blood pressure will be recorded to the nearest mmHg.

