As a component of limited physical exam by Investigator and during the solicited reporting periods, reactogenicity events will be assessed with results reported in the eDiary post-IP administration. If a Grade 3 or 4 local reaction is reported in the eDiary then the site Investigator must contact the subject within 18 hours to discuss the symptom in detail and confirm the scoring. Following an eDiary report of a Grade 3 or 4 local reaction, the site will determine whether additional action such as a site visit is warranted. If a Grade 4 local reaction is reported then the Investigator or trained medical professional must confirm the score and must immediately notify the Sponsor.

Please score reactions as follows:

Local reaction	Mild (Grade 1)	Moderate (Grade 2)	Severe (Grade 3)	Potentially Life Threatening (Grade 4)
Stuffy nose / Nasal congestion	Does not interfere with activity	Use of saline or other decongestant > 24 hours or interferes with activity	Repeated use of decongestants or significantly interferes with daily activity	Emergency room (ER) visit or hospitalization
Runny nose / Nasal rhinorrhea	Does not interfere with activity	Use of saline or other decongestant > 24 hours or interferes with activity	Significantly interferes with daily activity	Emergency room (ER) visit or hospitalization

Vital signs

Please score items based on the following guidance (from FDA Guidance for Industry: Toxicity Grading Scale for Healthy Adult and Adolescent Volunteers Enrolled in Preventive Vaccine Clinical Trials, September 2008) and note whether clinically significant:

Vital Signs *	Mild (Grade 1)	Moderate (Grade 2)	Severe (Grade 3)	Potentially Life Threatening (Grade 4)
Fever (°C) **	38.0 - 38.4	38.5 – 38.9	39.0 – 40	> 40
(°F) **	100.4 - 101.1	101.2 - 102.0	102.1 - 104	> 104
Tachycardia - beats per minute	101 – 115	116 – 130	> 130	ER visit or hospitalization for
				arrhythmia
Bradycardia - beats per minute***	50 – 54	45 – 49	< 45	ER visit or hospitalization for
				arrhythmia
Hypertension (systolic) - mm Hg	141 – 150	151 – 155	> 155	ER visit or hospitalization for
				malignant hypertension
Hypertension (diastolic) - mm Hg	91 – 95	96 – 100	> 100	ER visit or hospitalization for
				malignant hypertension
Hypotension (systolic) – mm Hg	85 – 89	80 - 84	< 80	ER visit or hospitalization for
				hypotensive shock
Respiratory Rate – breaths per minute	17 - 20	21 – 25	> 25	Intubation

^{*} Subject should be at rest for all vital sign measurements.

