1. STATISTICAL METHODS PLANNED IN THE PROTOCOL AND DETERMINATION OF SAMPLE SIZE

The objective of this analysis plan is to describe the planned study analyses. Where the protocol and this SAP disagree, the SAP takes precedence. This SAP is to be finalized prior to locking the clinical database.

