9.2. Adverse Events (AEs)

Adverse events were to be recorded from the day of informed consent through QIV Day 29. For subjects without QIV administration, follow-up for both AEs and SAEs was 28 days after IP. During the study treatment period subjectswere asked non-leading questions to determine the occurrence of spontaneously reported (unsolicited) AEs.

Symptoms were collected for the 7 days following IP administration using eDiaries, with clinical interpretation of data entries by the site investigator. At the discretion of the investigator, a symptom recorded by the subject on the eDiary may have been reported as an AE. The investigator was responsible for determining the severity and the relationship to IP for any eDiary-based AEs. There was no reconciliation of the database between the eDiary symptoms and other AE reports.

PE findings recorded as clinically significant, severe, or life threatening were to be recorded as AEs. Investigators usedtheir judgement regarding reporting of additional PE findings as AEs.

All AEs will be included in the listings. Only treatment emergent AEs will be summarized.

Separate listings of subjects who died, discontinued the study due to an AE, or experienced an SAE will be provided.

Treatment-emergent AEs (TEAE) are AEs with start dates between administration of the IP and IP Day29. If there is no administration of QIV then AE/SAE follow-up will be 28 days post IP administration. However, AEs with start dates past Day 29, if judged by the investigator to be IP-related, will be included in the treatment emergent set.

All AEs will be coded based on MedDRA (V24.0).

Where provided in Protocol Appendix 1, AEs will be graded according to the Vital Sign and Systemic Toxicity Assessments.

N (%) of subjects with at least one TEAE and N (%) of subjects with at least one treatment-related treatment-emergent AE (TRAE) will be summarized. TEAE and TRAE by worst severity will be summarized.

N (%) of subjects with TEAE will be reported by System Organ Class and Preferred Term (SOC/PT) and maximum severity. N (%) of subjects with TRAE will be reported by SOC/PT and maximum severity.

N (%) of subjects with TEAE by SOC/PT by overall frequency (decreasing) will be reported.N (%) of subjects with TRAE will be reported by SOC/PT by overall frequency (decreasing).

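### SAP 9.4 lists diastolic instead of systolic hypotension for the graded shift tables, leaves the source of respiratory rate unexplained, and provides no worst-grade shift for the IP period alone

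*SAP*

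**What the plan says.** SAP 9.4 plans two displays. In the first, "Blood pressures, heart rate, respiratory rate and temperature will be summarized at each time point by descriptive statistics", as the result and as change from the IP baseline and then the QIV baseline. In the second, graded vital signs are reported as "shift tables of worst grade recorded post IP administration through QIV Day 29". The graded parameters are fever, tachycardia, bradycardia, "systolic and diastolic hypertension, diastolic hypotension, and respiratory rate". The grading source named is the FDA 2008 toxicity scale.

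Protocol Appendix 2 reproduces vital-sign grades from that guidance. Its only low-pressure row is "Hypotension (systolic) – mm Hg". It also has a respiratory-rate row. Protocol 6.2.1.5 describes what is measured: "Vital signs include oral temperature (°C), blood pressure (mmHg), pulse rate (beats per minute"). Tables 2 and 3 likewise show blood pressure, heart rate and temperature only.

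Three other SAP statements bear on this:
- SAP 1: "Where the protocol and this SAP disagree, the SAP takes precedence".
- SAP 5 defines a second, QIV baseline for vital signs, and SAP 9.2 reports AEs separately before and after QIV.
- SAP 9.2: "Where provided in Protocol Appendix 1, AEs will be graded according to the Vital Sign and Systemic Toxicity Assessments".

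**The concern.** Vital signs are a named safety assessment under the primary objective, and the shift table is the display that shows individual subjects moving into a graded category. Three features of SAP 9.4 weaken it.

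1. The hypotension parameter does not match the grading scale. A programmer following the text has no cut-points for the parameter listed and no instruction to tabulate the one that does have cut-points. The SAP's precedence clause means the protocol does not automatically correct this.
2. Respiratory rate is requested in both displays, but the protocol schedules no such measurement.
3. A single worst grade over the whole period cannot show whether a grade was reached after IP alone or only after QIV. Elsewhere the SAP makes that separation, for AEs and for change from baseline.

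The SAP 9.2 cross-reference adds to the first problem. It sends the reader to Appendix 1 for vital-sign and systemic grades, but Appendix 1 is the eDiary form and contains no vital-sign grades. The SAP text supplied never cites Appendix 2. SAP 1.1.2.3 also gives the statistician and programmers access to treatment codes throughout the trial, so substitutions of this kind are better fixed in writing than settled during programming.

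**Working it through.** The plan states no figure on this point, so there is none to reproduce. The check is a comparison of the texts, followed by a count of readings.

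**Step 1. Parameters side by side**

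| Parameter | In SAP 9.4 shift list | Graded in Appendix 2 | Measurement scheduled (6.2.1.5, Tables 2 and 3) |
|---|---|---|---|
| Fever | yes | yes | yes |
| Tachycardia | yes | yes | yes |
| Bradycardia | yes | yes | yes |
| Systolic hypertension | yes | yes | yes |
| Diastolic hypertension | yes | yes | yes |
| Systolic hypotension | **no** | yes (85–89 / 80–84 / <80 mm Hg) | yes |
| Diastolic hypotension | yes | **no** | yes |
| Respiratory rate | yes | yes (17–20 / 21–25 / >25 / intubation) | **no** |

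The SAP lists seven parameters and Appendix 2 has seven rows. Five agree in all three columns. One Appendix 2 row is missing from the SAP, one SAP entry has no grade, and one entry has a grade but no scheduled measurement. SAP 12, which lists changes to conduct and analysis, mentions none of these.

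**Step 2. Scheduled readings in the shift-table window**

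- After IP and before QIV: V01 at about 15 minutes after dosing, V02 and V03, which makes 3. V04 vital signs are taken before QIV dosing and add a fourth when V04 is a separate visit.
- After QIV: V05 only.
- Total through QIV Day 29: 4 + 1 = 5 with separate visits, or 3 + 1 = 4 when V03 and V04 fall on one day. SAP 8.2 says IP Day 29 and QIV Day 1 samples were collected on the same day for about 40% of subjects.

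The pooled window therefore adds exactly one scheduled reading per subject, plus any unscheduled ones.

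**Step 3. How much one extra reading can matter**

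The documents give no rate of graded readings. Assume that each reading has chance p of being graded and that readings are independent. The chance of at least one graded reading among k is 1 − (1 − p)^k.

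| Assumed p | k = 3 | k = 4 | k = 5 |
|---|---|---|---|
| 0.02 | 5.9% | 7.8% | 9.6% |
| 0.05 | 14.3% | 18.5% | 22.6% |
| 0.10 | 27.1% | 34.4% | 41.0% |
| 0.20 | 48.8% | 59.0% | 67.2% |

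At p = 0.10, adding V05 moves the figure from 34.4% to 41.0% with separate visits, since 0.9^4 × 0.1 = 6.6 points. With combined visits it moves from 27.1% to 34.4%, since 0.9^3 × 0.1 = 7.3 points. Readings on one person tend to agree, so the real increase would usually be smaller. This is an illustration, not an estimate for the trial.

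**The case against.** There is a fair case that much of this is minor.

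- **Hypotension.** The SAP introduces its list as what the assessed signs include, so the list may not be exhaustive, and diastolic is probably a slip for systolic. A reader might infer that low systolic pressure would go unreported. The documents do not support that. Blood pressures are summarised at every time point, and clinically significant values or changes could be recorded as AEs at the investigator's discretion. What is at risk is the graded shift row. That part stands, because the SAP overrides the protocol and the text as written is wrong.
- **Respiratory rate.** A reader might infer that the row cannot be produced and should be deleted. That is not established. Appendix 2 does grade respiratory rate. The SAP is dated June 2022, after the planned end of follow-up, and is based on protocol v2.0, whereas the protocol reviewed here is v3.0. SAP 9.1 shows that its authors knew what the eCRF captured for dosing. The eCRF is not among the documents, so respiratory rate may have been recorded. What stands is that the source is unexplained.
- **Pooled window.** A reader might infer that QIV effects contaminate the vaccine-versus-placebo comparison. Both arms receive QIV, so post-QIV readings enter both columns. The safety aim in protocol 8.3 covers the vaccine alone and when followed by licensed vaccine, and a window through QIV Day 29 serves the second part. The time-point summaries already use both baselines. SAP 9.4 does not say which baseline the shift tables use, so it cannot be assumed to be the IP baseline. What stands is narrower: there is no worst-grade display for the vaccine-alone part of that aim.
- **Weight.** No vital-sign measure is among the primary endpoints in protocol 2.2.1, and no formal hypotheses are tested.

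**Conclusion.** The concern holds in a limited form. The hypotension entry is an error as written: one of seven graded Appendix 2 rows is omitted from the shift tables and an ungraded parameter stands in its place. Respiratory rate is an unresolved inconsistency between the SAP and the protocol's schedule of measurements. The single window is a real but modest loss of information: one scheduled post-QIV reading per subject, in both arms, and no IP-only worst-grade shift.

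None of this affects a primary endpoint or removes blood pressure from the report. The conclusion rests on the SAP and protocol texts as supplied, on Appendix 2 being a faithful copy of the scale the SAP names, and on the visit schedule in Tables 2 and 3. The percentages above depend on assumed rates and show only the order of size. Correction is worthwhile because these tables support the primary safety objective and the change is cheap.

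**What to change.** Amend the SAP as follows.

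1. In 9.4, replace diastolic hypotension with systolic hypotension, graded by Protocol Appendix 2.
2. In 9.4, reconcile respiratory rate with protocol 6.2.1.5 and Tables 2 and 3. State where the data come from, or remove the parameter from both displays if it was not collected.
3. Replace the single shift table with two: IP baseline to worst grade after IP and before QIV; and QIV baseline to worst grade after QIV through QIV Day 29. Name the baseline in each title. The pooled table may be kept as well, for the aim that covers vaccine followed by licensed vaccine.
4. In 9.2, change the grading cross-reference from Appendix 1 to Appendix 2.

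The cost is a few words and one extra descriptive table. No new data are needed, and both baselines are already defined. With one scheduled post-QIV reading, the second table will largely be a V04-to-V05 shift.
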